Collection of reportable concomitant medications	X	X		X		X
Collection of pregnancies	X	To be reported at any time during the study				
End of Active Phase participation record	X					X

Abbreviations: AE: adverse event; AESI: adverse events of special interest; AF: Assent Form; BL: blood sampling; CRF: Case Report Form; DC: diary card; ICF: Informed Consent Form; IM: intramuscular; IRT: interactive response technology; SAE: serious adverse event; TC: telephone call

\* Physical examination should be performed as per standard of care including, but not limited to, a general examination of the main body systems of interest (ie, heart, lung, skin, neurologic, muscular-skeletal, lymphatic system, etc). Temperature to be measured by oral (preferred route), rectal, or axillary route using a digital thermometer before vaccination and daily during the 7 days after vaccination and recorded in the diary card. If a routine examination had been performed within the last week by the Investigator, a sub-Investigator, or a licensed nurse practitioner, it does not need to be repeated unless there were some changes in health status, in which case it may be limited to the affected area.

† Should a participant receive oral or injectable antibiotic therapy within 3 days prior to any blood draw, the Investigator will postpone that blood draw until it has been 3 days since the participant last received oral or injectable antibiotic therapy. Postponement must still be within the timeframe for blood draw. If postponement would result in the sample collection falling outside of this timeframe, the blood sample should be collected without postponement, and it should be appropriately documented that the sample was taken less than 3 days after stopping antibiotic treatment.

¥ Blood sample corresponding to the rSBA subset of participants.

‡ Blood sample at Day 01 and Day 31 will be drawn before administration of the vaccines.

§ This call is made 8 days to 10 days after the respective vaccinations. If Day 09 (+2 days) or Day 39 (+2 days) falls on a weekend or holiday, the telephone call may be made on the following business day. During this telephone call, the staff will find out whether the participant experienced any SAE (including any AESI) not yet reported, and will remind the participant's parent/legally acceptable representative to continue using the diary card, bring the diary card to the study center at the next visit, and confirm the date and time of the next visit.

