## 6.5 Concomitant Therapy

At the time of enrollment, ongoing medications and other therapies (eg, blood products) should be recorded in the source document as well as new medications prescribed for new medical conditions/AEs during study participation.

Documentation in the CRF of ongoing concomitant medication will be limited to specific categories of medication of interest beginning on the day of first vaccination. This may include medications of interest that were started prior to the day of vaccination.

---

a All unexpected and related SAEs submitted to European Union and Asian competent authorities must be unblinded.

Reportable medications (Category 1, 2, and 3) will be collected in the source document from the day of first vaccination to the end of the studya and in the CRF as per the instructions given below for each category.

Reportable medications include medications that impact or may impact the consistency of the safety information collected after any vaccination and/or the immune response to vaccination. Three standard categories of reportable medications are defined:

- Category 1: medications impacting or that may have an impact on the evaluation of the safety (eg, antipyretics, analgesics, and non-steroidal anti-inflammatory drugs [NSAIDs], systemic steroids/corticosteroids [therapy duration less than 2 weeks], and other immune-modulators) Category 1 medication do not define the Per-Protocol Analysis Set (PPAS).

*Note: Topical steroids (inhaled, optic, ophthalmic, nasal, etc.) should not be captured or reported.*

- Category 1 medications will be reported in the CRF from the day of each vaccination to the end of the solicited and unsolicited follow-up period after each vaccination.
- Category 2: medications impacting or that may have an impact on the immune response and used to define the PPAS; for example:
  - Flu vaccines administered within 14 days pre or post each trial vaccination, including the day of the study vaccination visit
  - Any vaccine (including COVID-19 vaccine) other than study vaccines (vaccines not described in the Protocol) within the 28 days (4 weeks) preceding or after the trial vaccination, including the day of the study vaccination visit
  - Immune globulins, blood or blood-derived products: used in the 3 months preceding the first blood draw and up to the last blood draw

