  - Immunosuppressive therapy such as immune-suppressors, immune-modulators with immunosuppressive properties, long-term systemic corticosteroids therapy (prednisone or equivalent for more than 2 consecutive weeks) used in the past 3 months preceding the study vaccination and up to the last blood draw, anti-cancer chemotherapy, anti-proliferative drugs such as deoxyribonucleic acid (DNA) synthesis inhibitors, or radiation therapy: used in the 6 months preceding the first study vaccination, and up to the last blood draw

Category 2 medications will be reported in the CRF during the study period and up to the last blood draw.

- Category 3: systemic (oral or injectable) antibiotics received within 72 hours preceding each visit for blood draw related to IMP assessment (meningococcal vaccines) and used to define

---

a Participant's parents/legally acceptable representatives will be required to document all medications received in the diary cards. The sites will focus on only recording the medications belonging to the 3 categories in the other source documents.

the PPAS, as they may interfere with bioassays used for antibody testing when taken before a blood draw

Category 3 medications will be reported in the CRF for the period of 3 days (72 hours) before each blood draw.

*Note: Topical antibiotics (Inhaled, optic, ophthalmic, nasal, etc.) should not be captured or reported.*

The information reported in the CRF for each reported medication will be limited to:

- Trade name
- Rationale for the origin of prescription: Whether it was a prophylactica medication? Prophylactic medications will be recorded in the Action Taken section of the AE collection tables.
- Medication category (1, 2, or 3)
- Start and stop dates

Dosage and administration route, homeopathic medication, topical and inhaled steroids, as well as topical, ophthalmic, and ear treatments will not be recorded. Topical analgesics should not be applied at the site of vaccination; however, if they are applied inadvertently to the vaccination site, they should be recorded as a Category 1 medication in this specific instance.

If the participant has received medications other than those listed in Categories 1, 2, and 3, the detailed information will be collected in the source documents only.

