	
 
Participant received a protocol-prohibited therapy/medication /vaccine (Category 2 or Category 3)
 
Participant had other protocol violations that affected the participant's immune response, as determined by the clinical team before locking the database
 
 
In addition, to the reasons listed above, participant will also be excluded from the hSBA PPASM if:
 
 
Participant serology samples did not produce a valid test result (ie, hSBA result for all meningococcal antigens are missing)
 
 
And from rSBA PPASM if:
 
 
Participant serology samples did not produce a valid test result (ie, rSBA result for all meningococcal antigens are missing)
 
 
PPASC:
 
Participants presenting with at least 1 of the following relevant protocol deviations will be excluded from the PPASC:
 
 
Participant did not meet all protocol-specified inclusion criteria or met at least 1 of the protocol-specified exclusion criteria
 
Participant did not complete the vaccination schedule
 
Participant received a vaccine other than the one that he/she was randomized to receive
 
Preparation and/or administration of vaccine was not done as per-protocol
 
Participants did not receive the vaccine in the proper time window: 
 
Visit 2: Visit 1 + 30 days [+14 days] (Group 1 and 2)
 
 
 
Participant did not provide a post-dose serology sample in the proper time window or a post-dose serology sample was not drawn: 
 
Blood sampling 3 (BL03AA) in Group 1 and 2:
 
Visit 3: Visit 2 + 30 days [+14 days]
 
Blood sampling 3 (BL03BB or BL03BR) in Group 3:
 
 
 

Population	Description

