	
 
• Visit 3: Visit 1 + 30 days [+14 days]
 
• Participant received a protocol-prohibited therapy/medication /vaccine (Category 2 or Category 3)
 
• Participants with their serology samples that did not produce a valid test result (ie, results for all antigens contained in 9vHPV and Tdap-IPV vaccines are missing)
 
• Participant had other protocol violations that affected the participant's immune response, as determined by the clinical team before locking the database
 
 
In the event of a local or national immunization program (eg, with a pandemic influenza vaccine or COVID-19 vaccine), participants who receive 1 or more doses of pandemic influenza vaccine or COVID-19 vaccine at any time during the study will not be withdrawn from the study.
 
If the participant receives the COVID-19 vaccine within this period of 28 days pre or post IMP vaccination (including the day of the study visit for IMP vaccine), she/he will be excluded from the PPAS population but will not be excluded from the study.

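### Minor: in Groups 1 and 2 the Category 2 windows that define PPASM run past the meningococcal post-dose sample, so some events after that sample remove a valid titre

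*Protocol*

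**What the plan says.** Protocol 9.3 lists the deviations that exclude a participant from the hSBA and rSBA PPASM. One is "Participant received a protocol-prohibited therapy/medication /vaccine (Category 2 or Category 3"). The set for the concomitant vaccines (PPASC) has the same bullet. Neither gives a time limit, so the limits come from 6.5:

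- Influenza vaccine: "Flu vaccines administered within 14 days pre or post each trial vaccination".
- Immune globulins and blood products: "used in the 3 months preceding the first blood draw and up to the last blood draw".
- Immunosuppressive and anti-cancer therapy: "used in the 6 months preceding the first study vaccination, and up to the last blood draw". Long-term systemic corticosteroids also count up to the last draw.
- Any other non-study vaccine, including COVID-19: "within the 28 days (4 weeks) preceding or after the trial vaccination, including the day of the study vaccination visit".

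Category 3 (antibiotics) is narrower. It counts before "each visit for blood draw related to IMP assessment (meningococcal vaccines").

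A closing sentence in 9.3 adds: "If the participant receives the COVID-19 vaccine within this period of 28 days pre or post IMP vaccination", the participant leaves the PPAS but stays in the study. It does not say which of the three per-protocol sets is meant.

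Groups 1 and 2 receive the meningococcal vaccine at Visit 1, and 9vHPV with Tdap-IPV at Visit 2. Their PPASM post-dose sample is BL02 at Visit 2, and their last draw is BL03 at Visit 3. The footnote to Table 1.1 fixes the order at Visit 2: "Blood sample at Day 01 and Day 31 will be drawn before administration of the vaccines". In Group 3 the last draw is also the meningococcal post-dose sample.

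**The concern.** PPASM and PPASC rest on different samples in Groups 1 and 2, and their bullets on sampling and vaccination differ accordingly. The Category 2 bullet was not adapted. In PPASM it therefore uses windows that suit a set ending at BL03, although the titre being analysed was fixed at BL02. A product first received after BL02 cannot change that titre, so excluding the participant loses a valid primary-endpoint result for no scientific gain.

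At stake is the size of the per-protocol set on which 9.2 bases the power, and whether two programmers would derive the same set.

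**Working it through.** **Windows, in days after Visit 1 (Groups 1 and 2).** Visit 2 and BL02 fall at 30 to 44 (Table 1.1). BL03 follows BL02 by 30 to 44 days.

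| Category 2 item | End of window | Time after BL02 in which it still excludes |
|---|---|---|
| Influenza vaccine | 30+14 = 44 to 44+14 = 58 | 14 days |
| Blood products, immunosuppressants | BL03: 30+30 = 60 to 44+44 = 88 | 30 to 44 days |
| Other vaccines, if Visit 2 counts | 30+28 = 58 to 44+28 = 72 | 28 days |
| Other vaccines, if only Visit 1 counts | 28 | none |

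In Group 3 the vaccine windows end by day 28, before the sample at 30 to 44, and the last draw is that sample. No Category 2 event after the sample can exclude there.

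**The two readings for other vaccines.** The 28-day window in 6.5 refers to one trial vaccination in the singular, whereas the influenza window refers to each. Category 3 glosses IMP assessment as the meningococcal vaccines. Both favour Visit 1 only. Table 6.1, however, labels all four vaccines as IMP, which brings in Visit 2. The text does not decide.

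**The plan's own power.** Inputs from 9.2 and Table 9.1: 155 per group, margin 0.10, one-sided alpha 0.025, equal rates of A 0.935, C 0.985, Y 0.972 and W 0.991. The Farrington-Manning power is Φ[(0.10 − 1.960·SE0)/SE1], with SE0 taken at the rates fitted under a difference of −0.10. For serogroup A those rates are 0.859 and 0.959:

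- SE0 = √[(0.859·0.141 + 0.959·0.041)/155] = 0.0321
- SE1 = √[2·0.935·0.065/155] = 0.0280
- Power = Φ(1.32) = 90.7%, as in Table 9.1

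Y gives 99.3%, and C and W exceed 99.9%. The product over the four is 90.1%, in line with the stated overall figure of at least 90%.

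**Power of the planned analysis.** Section 9.4.2 uses the Newcombe interval. Power is the exact binomial probability that its lower 95% limit exceeds −0.10, multiplied over the four serogroups (independence assumed). At 155 per group: A 92.6%, C 99.98%, Y 99.5%, W 100.0%; product 92.1%.

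| Per group | Further loss from 155 | Overall power |
|---|---|---|
| 155 | 0 | 92.1% |
| 152 | 3 | 91.5% |
| 147 | 8 | 90.2% |
| 146 | 9 | 90.1% |
| 145 | 10 | 89.8% |
| 139 | 16 | 88.5% |
| 124 | 31 | 83.2% |

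Every size from 146 to 155 gives at least 90%. The first shortfall is at 145: 10/155 = 6.5% further loss, or (174 − 145)/174 = 29/174 = 16.7% in all. The plan states 10%; its 155 corresponds to 19/174 = 10.9%.

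On the Farrington-Manning planning formula there is almost no slack (90.1% at 155, 89.2% at 151), but the trial will be judged by the Newcombe interval.

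**The case against.** **The bullet can be read by purpose.** The list is introduced as relevant deviations, and Category 2 is defined by its effect on the immune response, so an event after BL02 could be thought irrelevant to PPASM. This does not settle it. The same lead-in says that participants with a listed deviation will be excluded, and clinical-team judgement is given only for other, unlisted violations.

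**The fuller SAP may settle it.** This stands. The supplied SAP covers only the safety (SMT) analysis and marks the PPAS as not applicable (SAP 3.3). Protocol 9 and 9.4 promise a more detailed SAP before database lock, which is not among the documents.

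**The events should be uncommon.** This also largely stands. E04 bars planned vaccines in the 4 weeks after any study vaccination, and E08 and E19 screen out immunodeficiency, recent immunosuppression and interfering chronic illness. The dropout allowance is stated as loss from the PPAS, so it already includes whatever Category 2 exclusions the sponsor expected. Section 9.2 lets the sample size grow. E04 does not, however, stop unplanned vaccination, or a blood product or immunosuppressant needed after BL02.

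**Independence is an assumption.** Positive correlation between serogroups would raise joint power above the product. Serogroup A alone has 90.5% at 145, so the break-even could move slightly further out.

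**Section 7.1.3 may seem to conflict**, because it keeps participants vaccinated in national programmes in the study. It does not: 9.3 separates leaving the PPAS from leaving the study.

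**Conclusion.** The point holds as a minor one. On the literal text, influenza vaccine within 14 days after Visit 2, or a blood product or immunosuppressant first used between BL02 and BL03, takes a Group 1 or 2 participant out of PPASM with no bearing on the titre analysed. For other vaccines, including COVID-19, this is so only if Visit 2 counts as the reference vaccination.

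A reader might go further in three ways that the documents do not support:

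- **Biased primary comparison.** The rule and schedule are the same in Groups 1 and 2, both are observer-blind, and 9.4.1 also plans the FAS analysis, which keeps these participants. The contrast with Group 3 touches descriptive results only.
- **Any influenza vaccine after Visit 2 excludes.** The window is 14 days.
- **The trial is underpowered.** No event rate is given. With the Newcombe interval and independent serogroups, 90% holds for up to 9 further losses per group below 155 and first fails at 10.

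What remains is avoidable loss of per-protocol size, of unknown and probably small extent, and uncertain PPASM membership after a COVID-19 or other vaccine.

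**What to change.** Before database lock, state in the immunogenicity SAP:

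- For hSBA and rSBA PPASM, Category 2 items count only up to the meningococcal post-dose sample (BL02 in Groups 1 and 2, BL03 in Group 3), with the vaccine windows tied to the Visit 1 vaccination.
- For PPASC, the Visit 2 windows and the last-draw limit stay.
- In the COVID-19 rule, the vaccination and the analysis set are named.

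Carry the same wording into Protocol 6.5 and 9.3 at the next amendment; no amendment is needed for this alone.

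Tying the vaccine windows to Visit 1 also stops counting influenza vaccine given in the 14 days before Visit 2 but more than 14 days after Visit 1. Group 3 is already treated this way. The sponsor should confirm that this is intended.

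The cost is a small change to the PPASM derivation. No visit, sample or new data item is needed, because start and stop dates of Category 2 items are already in the CRF (6.5).

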## 9.4 Statistical Analyses

The SAP will be finalized prior to database lock and it will include a more technical and detailed description of the statistical analyses described in this section. This section is a summary of the planned statistical analyses of all the endpoints including primary, secondary, and observational endpoints.

### 9.4.1 General Considerations

Immunogenicity analyses will be performed on the appropriate PPAS and FAS. Safety analysis will be performed on the SafAS.

### 9.4.2 Primary Hypotheses and Methods

For primary endpoint, refer to [Section 3](#).

The primary objective will be met if the following null hypothesis is rejected for each of the 4 serogroup A, C, W, Y:

$$H_0: p_{\text{MenACYW}} - p_{\text{Nimenrix}} \leq -0.1$$

$$H_1: p_{\text{MenACYW}} - p_{\text{Nimenrix}} > -0.1$$

where  $p_{(MenACYW)}$  and  $p_{(Nimenrix)}$  are the percentages of participants who achieve an hSBA titer  $\geq 1:8$  in the MenACYW conjugate vaccine group and the comparator group (Nimenrix®), respectively.

The 95% confidence interval (CI) of the difference in proportion will be computed using the Wilson Score method without continuity correction (Newcombe method) (40).

If the lower limit of the 2-sided 95% CI of the difference between the 2 percentages is  $> -0.1$ , the non-inferiority will be demonstrated.

Non-inferiority will be demonstrated if all 4 individual null hypotheses (4 serogroups) are rejected.

#### 9.4.3 Secondary Hypotheses and Methods

##### *Immunogenicity*

For secondary immunogenicity endpoints, refer to [Section 3](#).

The statistical analysis for secondary objectives will be descriptive.

In general, categorical variables will be summarized and presented by frequency counts, percentages, and CIs. The 95% CIs of percentages will be calculated using the exact binomial distribution (Clopper-Pearson method). For geometric mean titer and geometric mean concentration, 95% CIs of point estimates will be calculated using a normal approximation assuming they are log-normally distributed.

##### *Safety*

For secondary safety endpoints, refer to [Section 3](#).

Safety results will be described for participants in all study groups. The main parameters for the safety endpoints will be described by frequency counts and 95% CIs (based on the Clopper-Pearson method).

#### 9.4.4 Observational Endpoints

For observational endpoints, refer to [Section 3](#).

The statistical analysis for observational objectives will be descriptive and will be carried out similar to the secondary immunogenicity analysis described in [Section 9.4.3](#). More details about statistical analyses of observational objectives will be given in the SAP.

#### 9.4.5 Sensitivity analysis due to COVID-19 pandemic

The impact of COVID-19 pandemic situation on study conduction will be summarized through impact on visit procedures, study completion and major/critical protocol deviations due to COVID-19. The participants impacted by COVID-19 pandemic situation will be defined as the participants with at least one major/critical protocol deviation due to COVID-19 or who did not complete the study due to COVID-19. If more than 10% of participants are impacted as per this

definition, the main immunogenicity and safety endpoints will also be summarized in these participants to assess the impact of COVID-19 situation on the study outcome.

## **9.5 Interim Analyses**

This study will not include an early safety data review. However, participant safety will be continuously monitored by the Sponsor's internal safety review committee which includes safety signal detection at any time during the study.

No analyses are planned to be performed prior to the formal completion of the study.

## **9.6 Data Monitoring Committee**

Not applicable.

## 10 Supporting Documentation and Operational Considerations

### 10.1 Appendix: Regulatory, Ethical, and Study Oversight Considerations

Note: The term “participant” is used throughout this protocol. However, the term “participant” will be used in the CRF in order to comply with the Clinical Data Interchange Standards Consortium requirements.

### 10.2 Regulatory and Ethical Considerations

- This study will be conducted in accordance with the protocol and with the following:
  - Consensus ethical principles derived from international guidelines including the Declaration of Helsinki and Council for International Organizations of Medical Sciences International Ethical Guidelines
  - Applicable ICH Good Clinical Practice (GCP) Guidelines
  - Applicable laws and regulations (eg, data protection law as General Data Protection Regulation [GDPR])
- The protocol, protocol amendments, ICF, Investigator Brochure, and other relevant documents (eg, advertisements) must be submitted to an IEC/IRB by the Investigator or the Sponsor (according to local regulations) and reviewed and approved by the IEC/IRB before the study is initiated
- Any amendments to the protocol will require IEC/IRB approval before implementation of changes made to the study design, except for changes necessary to eliminate an immediate hazard to study participants
- The Investigator will be responsible for the following:
  - Providing written summaries of the status of the study to the IEC/IRB annually or more frequently in accordance with the requirements, policies, and procedures established by the IEC/IRB.
  - Determining whether an incidental finding (as per Sanofi policy) should be returned to a participant and, if it meets the appropriate criteria, to ensure the finding is returned (an incidental finding is a previously undiagnosed medical condition that is discovered unintentionally and is unrelated to the aims of the study for which the tests are being performed). The following should be considered when determining the return of an incidental finding:
    - The return of such information to the study participant (and/or his/her designated healthcare professional, if so designated by the participant) is consistent with all applicable national, state, or regional laws and regulations in the country where the study is being conducted, and

- The finding reveals a substantial risk of a serious health condition or has reproductive importance, AND has analytical validity, AND has clinical validity.
- The participant in a clinical study has the right to opt out of being notified by the Investigator of such incidental findings. In the event that the participant has opted out of being notified and the finding has consequences for other individuals, eg, the finding relates to a communicable disease, Investigators should seek independent ethical advice before determining next steps.
- In case the participant has decided to opt out, the Investigator must record in the site medical files that she/he does not want to know about such findings.
- Notifying the IEC/IRB of SAEs or other significant safety findings as required by IEC/IRB procedures.
- Providing oversight of the conduct of the study at the site and adherence to requirements of 21 CFR, ICH guidelines, the IEC/IRB, European regulation 536/2014 for clinical studies (if applicable), and all other applicable local regulations.

